6.5.9 Additional Sensitivity Analyses of Primary and Key Secondary Outcomes

Sensitivity analyses of primary and key secondary efficacy outcomes are the same as specified in the M-SAP.

6.5.10 Subgroup Analyses

In addition to the subgroups specified in the M-SAP, the following additional subgroups will be analyzed in the random-slope model (see Section 6.5.3) for primary and secondary efficacy endpoints in the FAS analysis set:

- Baseline use of riluzole and edaravone (neither, riluzole only, edaravone only, both),
- Age (less than 65 years vs. 65 years or older),
- Sex (female vs. male),
- Race (white vs. any minority race with greater than 5% prevalence in the sample),
- Ethnicity (Hispanic or Latino vs. non-Hispanic or Latino),
- Weight (less than 43 kg, 43 to less than 56 kg, 56 to less than 77 kg, 77 to less than 150 kg, 150 kg or more),
- BMI (less than 18.5 kg/m², 18.5 to less than 25 kg/m², 25 to less than 30 kg/m², 30 to less than 40 kg/m², 40 kg/m² or more),
- Chronic kidney disease (CKD) stage (stage 1 or better [eGFR 90 mL/min/1.73m² or more], stage 2 [eGFR 60 to 89 mL/min/1.73m²], stage 3 [eGFR 30 to 59 mL/min/1.73m²], stage 4 [eGFR 15 to 29 mL/min/1.73m²], stage 5 [eGFR less than 15 mL/min/1.73m²]),
- Time since onset of weakness (less than 18 months vs. 18 months or longer),
- El Escorial and time since onset of weakness (El Escorial definite and less than 18 months vs. not both),
- Baseline symptom severity (all ALSFRS-R questions scored 2 or greater vs. any question scored 0 or 1),
- Early disease state (all ALSFRS-R questions scored 2 or greater, SVC 80%-predicted or greater, and time since symptom onset less than 24 months vs. not meeting all three criteria),
- Baseline serum urate concentration (less than 5.5 mg/dL vs. 5.5 mg/dL or greater),
- Baseline serum NfL concentration (by median split), and
- Site (individual sites with at least 5 participants per treatment group and all participants from sites with fewer than 5 participants per treatment group pooled).

For each classification, unknown, not reported, and missing will be considered one group. All individuals not included in a specified subgroup will be combined into a mixed, "other" group. The "other" group will be included in analyses if its prevalence is greater than 5%; otherwise, the "other" group will be excluded.

In cases where a model for a given subgroup and endpoint fails to converge, the covariance terms for the regimen-specific random effects will be simplified from unstructured covariance of intercepts and slopes to separate, uncorrelated variance components for intercepts and slopes. If convergence still fails, regimen-specific intercepts and slopes will be modeled as fixed effects. If convergence still fails, the participant-specific random effects will be simplified from unstructured covariance of intercepts and slopes to separate, uncorrelated variance components for intercepts and slopes.

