5.6 Biofluid Biomarkers of Neurodegeneration

Blood biomarkers of neurodegeneration, including biomarkers of neuromuscular dysfunction, will be assayed. These will include serum creatinine and serum and CSF neurofilament light chain (NfL). Serum creatinine will be assayed by the kinetic Jaffe method (test 001370, Labcorp, Burlington, NC). NfL will be assayed by single-molecule array (Simoa; Quanterix, Billerica, MA). Levels of serum and CSF NfL that are reported to be below the limit of quantitation will be imputed at the limit of quantitation. Levels of serum and CSF NfL will be log-transformed in all analyses.

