- Population-level summary: difference in conditional means of active treatment relative to placebo.

Inference from this analysis is supportive of inference from the Bayesian shared-parameter, repeated-measures model for the primary endpoint and is the primary analysis for secondary endpoints. A separate supportive analysis will include centered baseline serum NfL level and the interaction of centered baseline serum NfL level and visit as additional covariates.

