The estimand estimated by the primary linear contrast of the random-slopes linear mixed model is the difference in mean rate of progression of a given continuous efficacy endpoint in the active treatment group relative to the placebo group in the FAS population. The estimand is defined by the following attributes:

Treatment: zilucopan administered subcutaneously once daily at a dosage of approximately 0.3 mg/kg vs. placebo.

Population: FAS population as defined in Section 6.1.

Variables: mean rate of change in endpoint from baseline to the Week 24 Visit.

Intercurrent event: treatment discontinuation: handled via treatment policy approach, all data will be used including data collected during the placebo-controlled period after treatment discontinuation. Missing data post-treatment will not be imputed, handled via missing at random assumption.

Population-level summary: difference in conditional mean slopes of active treatment relative to placebo.

Inference from these analyses is supportive of inference from the Bayesian shared-parameter, repeated-measures model for the primary endpoint and inference from the repeated-measures linear mixed model for secondary endpoints. A separate supportive analysis will include centered baseline serum NfL level and the interaction of centered baseline serum NfL level and study month as additional covariates.

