6.5.4 Survival and Time to Clinical Events

Survival and time to hospitalizations and clinical events will be analyzed in the FAS, ERO, EPP, STF, and SRO analysis sets. Survival analyses that include follow-up beyond the placebo-controlled period will be analyzed in the ERO analysis set. The summaries and analyses of time to death or death equivalent are the same as specified in the M-SAP with the addition of baseline age as an additional covariate in adjusted models, with the addition that the endpoints of time to death independent of occurrence of death equivalents and time to each of the hospitalization and clinical events will be separately analyzed using the same models, and with an additional adjusted analysis that includes baseline serum NfL level as a covariate. Analysis of time to

King's stage 4a or 4b will accommodate interval censoring between ALSFRS-R assessments and will be stratified by baseline King's stage.

Listings of all participants in the FAS, ERO, EPP, STF, and SRO analysis sets will document whether each participant had died, had reached a death equivalent endpoint, or was alive and free of a death equivalent and the study day of death, death equivalent, or last known alive and free of a death equivalent for each analysis timepoint.

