6.5.5 CAFS

The primary CAFS analysis is as specified in the MPRDR. Additional, unadjusted CAFS analyses are the same as specified in the M-SAP, including specification that pair-wise comparison of change in ALSFRS-R total score for participants who cannot be ranked by time to death or death equivalent is to the maximum follow-up time at which both participants have an observation, and with the following additions:

1. HHD upper and lower extremity percentage and SVC will be analyzed by CAFS by substituting change from baseline for those secondary efficacy endpoints in place of ALSFRS-R total score,
2. An additional set of CAFS analyses will use multiple imputation to extend follow-up of ALSFRS-R total score, HHD upper and lower extremity percentage and SVC for participants who early terminate, withdraw consent, or are lost to follow-up,
3. An additional set of CAFS analyses will use time to death alone independent of any death equivalent,
4. An additional set of CAFS analyses for ALSFRS-R total score, HHD upper and lower extremity percentage, and SVC will adjust rank scores in a linear model with the following covariates: time from ALS symptom onset, delta-FRS, baseline use of riluzole, and baseline use of edaravone, and
5. An additional set of CAFS analyses for ALSFRS-R total score, HHD upper and lower extremity percentage, and SVC will adjust rank scores in a linear model with the following covariates: time from ALS symptom onset, delta-FRS, baseline use of riluzole, baseline use of edaravone, and baseline serum NfL level..

The multiple imputation model used to extend follow-up of functional scores for participants who early terminate, withdraw consent, or are lost to follow-up will use linear regression with covariates of time since symptom onset, delta-FRS, baseline riluzole use, baseline edaravone use, and each observed functional score prior to a missing assessment.

Inference from CAFS analyses is supportive of inference from the Bayesian shared-parameter, repeated-measures model for the primary outcome and supportive of inference from the repeated-measures model for the secondary outcomes of HHD upper extremity score, SVC, and HHD lower extremity score. Primary inference from CAFS analyses will compare survival by time to death or death equivalent, will compare change in function to the last jointly observed time point, and will adjust for the specified covariates.

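### In the supplied documents, dependence of the treatment effect on baseline serum NfL is examined only through a median split; a continuous interaction term would use more of the information if the gradient is roughly linear

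*SAP*

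**What the plan says.** SAP 6.5.10 adds a list of subgroups to those in the Master SAP (M-SAP). It states that these "additional subgroups will be analyzed in the random-slope model (see Section 6.5.3) for primary and secondary efficacy endpoints", in the full analysis set. One entry is "Baseline serum NfL concentration (by median split". The section writes out no treatment-by-subgroup contrast, test or p-value for any entry.

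SAP 5.6 fixes the scale of the marker: "Levels of serum and CSF NfL will be log-transformed in all analyses".

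In the other efficacy analyses NfL is an adjustment covariate:
- Repeated-measures model (6.5.2): NfL and "the interaction of centered baseline serum NfL level and visit as additional covariates".
- Random-slopes model (6.5.3): NfL and "the interaction of centered baseline serum NfL level and study month as additional covariates", in a separate supportive analysis. The list of fixed terms in 6.5.3 also puts NfL and its month interaction in the main model, but the covariate vector and the SAS code omit them. No version has a treatment × NfL term.
- Survival and clinical events (6.5.4): an "additional adjusted analysis that includes baseline serum NfL level as a covariate".
- Combined assessment of function and survival (6.5.5): the fifth additional set adjusts rank scores for covariates ending in "baseline use of edaravone, and baseline serum NfL level".
- HHD0 and HHD0², voice measures and placebo multiple imputation (6.5.6 to 6.5.8): covariate only, with a B-spline interaction in the voice model.
- Comparison of controls (6.5.11): placebo participants only, so it says nothing about treatment effect.

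**The concern.** The plan already holds NfL as a continuous, log-transformed, centered covariate and has a random-slopes model that uses it in that form. For effect modification it turns the same variable into two halves. Participants just above and just below the median are then treated as different, while everyone within a half is treated as alike.

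The cut is also a sample statistic. The other continuous measures in the list (age, weight, BMI, eGFR, time since onset, urate) are cut at fixed values. The NfL cut depends on who is in the full analysis set, including shared placebo participants from regimens B, C and D, so it will not carry over to another sample.

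What is at stake is modest. If zilucoplan worked better at one end of the NfL range, a contrast between two halves would be less likely to show it, and would describe it less precisely, than a contrast using the measured values.

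**Working it through.** **The plan's own figure.** The documents give no power, precision or sample size for an NfL interaction, so there is nothing to reproduce.

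**Inputs.** From the SAP: the median split (6.5.10), the log scale (5.6) and the random-slopes model (6.5.3). Assumed: the shape of log NfL, a linear change in treatment effect with log NfL, and the same residual variance for both contrasts.

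**Formula.** Let X be centered log NfL and V the variable used in the interaction. With a true gradient β per unit of X, the noncentrality of the interaction test is k·β·Cov(X,V)/SD(V). Here k depends on the numbers per arm and the residual SD. For V = X this is k·β·SD(X). The ratio of the two is the correlation of X with V, so the relative efficiency is that correlation squared. Because k cancels, the 3:1 allocation and the number of shared placebo participants do not affect the relative loss.

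For a symmetric X and V = above or below the median, Cov(X,V) = E|X|/2 and SD(V) = 1/2. The correlation is therefore E|X|/SD(X).

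**Information kept by the split, under a linear gradient.**

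| Shape of log NfL | Kept | Lost | Source |
|---|---|---|---|
| Normal | (√(2/π))² = 0.637 | 36% | closed form |
| Uniform on (−1, 1) | (1/2)² / (1/3) = 0.75 | 25% | closed form |
| Logistic | 0.585 | 41.5% | 2 million draws |
| t, 5 df | 0.541 | 46% | 2 million draws |

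In the normal case, equal precision needs π/2 = 1.57 times the participants.

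**Power, normal case, two-sided 5%.** The noncentrality 1.960 + z(power) is multiplied by √(2/π) = 0.798. For 80%: (1.960 + 0.842) × 0.798 = 2.235, and 2.235 − 1.960 = 0.275, which is 61%.

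| Power, continuous term | Power, median split |
|---|---|
| 90% | 73% |
| 80% | 61% |
| 70% | 51% |
| 50% | 35% |
| 20% | 14% |

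The left-hand column is illustrative; the documents do not say where this trial would sit.

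**Other shape of effect.** If the true effect is a step exactly at the median, the split is the correct model and loses nothing. By the same squared correlation, the linear term then keeps only 64% in the normal case.

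**If the split also replaces NfL as the prognostic term.** The NfL gradient within each half then goes into the residual. A simulation assumed a prognostic slope of 0.5 residual SD and a linear interaction sized for about 80% power. Efficiency was 0.49 with 120 active and 40 placebo, and 0.54 with 120 active and an assumed 160 placebo. That is a loss of 51% and 46%. Section 6.5.10 does not say whether continuous NfL stays in the subgroup model, so this is a what-if.

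**The case against.** The strongest points on the other side are these.

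- **The plan tests no interaction here.** Section 6.5.10 asks for subgroup estimates only. This stands: the loss applies to whatever contrast a reader draws from the two halves. It also means the plan has no specified estimate of NfL effect modification.
- **Categorizing is the convention of the whole list.** Age, weight, BMI, eGFR, time since onset and urate are all cut. A prespecified median gives balanced groups, does not depend on the log transform, is little affected by setting values below the limit of quantitation to that limit, and leaves no later choice of cut-point. These are good reasons to keep the split as a display, but they do not make it the efficient estimate of a gradient.
- **The loss is conditional.** Nothing in the documents shows that log NfL is normal or that any gradient is linear. This stands, hence the range and the step case.
- **Starting power may be low.** With about 120 active and 40 placebo participants plus an unstated number of shared placebos, both versions could be weak. At an assumed 20%, the split costs about 6 points.
- **The M-SAP may contain a continuous analysis.** Sections 6.5.9 and 6.5.10 both defer to it. This cannot be excluded.

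A reader might also infer that NfL is the plan's main prognostic marker, and so the modifier most likely to be examined after a neutral result. The documents do not support that. Time since onset, delta-FRS, riluzole and edaravone are the core covariates, and NfL comes mainly in separate or additional analyses.

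**Conclusion.** The point holds as a low-priority improvement. Within the supplied documents, the median split is the only analysis that lets the treatment effect differ by NfL. For roughly normal log NfL and a linear gradient, an interaction contrast based on it keeps about 64% of the information, and 80% power becomes about 61%. The loss is roughly 25% to 46% for the other symmetric shapes tried and nil for a step at the median.

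Three stronger readings are not supported:
- **That 36% is a property of this trial.** It is a general result under assumptions the documents neither state nor contradict.
- **That the trial's conclusions are weakened.** The primary analysis is the Bayesian shared-parameter model (6.3). The secondary hierarchy (6.5.1) contains no subgroup contrast, so this analysis is exploratory.
- **That no continuous NfL interaction is planned anywhere.** That would need the M-SAP.

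**What to change.** In SAP 6.5.10, for NfL:

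1. Start from the random-slopes model with continuous NfL. Add treatment × centered log NfL and treatment × centered log NfL × month. Include NfL and NfL × month where they are not already present.
2. Name the three-way term as the estimate of NfL effect modification.
3. Report the active-minus-placebo slope difference with its 95% confidence interval at the 25th, 50th and 75th percentiles of NfL.
4. Keep the median split as a descriptive display.
5. Check linearity with tertiles or a quadratic or spline NfL term. Two groups cannot do this, because a straight line always fits two points.

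The cost is two further terms relative to the supportive NfL model of 6.5.3, or four relative to its printed SAS code. They apply to each endpoint a slope model can take: ALSFRS-R total, HHD upper extremity, HHD lower extremity and SVC. No new data are needed. The downside is a linearity assumption that has to be checked, and a less efficient estimate than the split if the true effect is a step near the median.

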6.5.11 Comparison of Controls across Regimens

Comparisons of placebo participants across regimens are the same as specified in the M-SAP with separate analyses that include baseline serum NfL level as an additional covariate in adjusted analyses plus applicable interaction terms as relevant to a given model.

6.5.12 Pharmacokinetic Analyses

Pre-dose concentrations of zilucoplan and its two major metabolites (RA102758 and RA103488) in plasma and CSF will be summarized by treatment group and visit in the ERO sample.

Concentrations below the limit of quantitation (BLQ) will be replaced with one half of the lower limit of quantitation. Summaries will include number of observations, number and percentage with concentrations BLQ, arithmetic mean, median, standard deviation, minimum, maximum, geometric mean, geometric coefficient of variation (calculated as $\sqrt{\exp(\text{variance of log-transformed concentrations}) - 1}$), and 95% confidence bounds for the geometric mean assuming log-normally distributed data.

Plasma concentration data of zilucoplan and its two major metabolites may be subjected to population pharmacokinetic analysis to derive population estimates of pharmacokinetic parameters and test the effect of various covariates such as anti-drug antibodies, age, weight, and sex. Details of the analysis will be described in a separate DAP. This analysis may be performed by combining data from the current study with data from other studies of zilucoplan, if deemed appropriate. The population pharmacokinetic analysis will be performed by UCB Ra Pharma and reported in a separate modelling report. The results of the population PK analysis will not be reported in the clinical study report (CSR).

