Zilucoplan shows species selectivity for non-human primate and human complement C5 only. The primary pharmacology of zilucoplan was established in vitro using direct binding and functional inhibition of complement assays, as well as enzyme-linked immunosorbent assays (ELISAs). Using surface plasmon resonance and analysis of a high-resolution co-crystal structure, zilucoplan has been shown to bind to a specific site on C5 and to exhibit a strong and rapid association with C5, as well as a slow dissociation rate. The binding site is distinct from that of the complement C5 inhibitor monoclonal antibody eculizumab and therefore is not affected by mutations in complement C5 known to prevent binding of eculizumab in patients of Asian and Han-Chinese descent (Nishimura et al. 2014). Target (C5) binding was confirmed using a competitive ELISA employing biotinylated zilucoplan to capture C5. Additionally, zilucoplan demonstrated dose-dependent inhibition of C5a and C5b formation following activation of classical or alternative pathways, as well as inhibition of RBC lysis in serum/plasma. Zilucoplan is a potent complement inhibitor in primates and humans and a weak/poor inhibitor in all other animal species tested (see below).

[figure not shown]
Species	IC ₅₀ (nM)
Human	6.6
Non-human primate	
Baboon	5.2
Chimpanzee	11.7
Cynomolgus	3.5
Rhesus	17.6
Dog	> 4,700
Rabbit	> 67,000
Porcine	
Mini-pig	51.9
Pig	118.6
Rodents	
Mouse	> 36,000
Rat	591.2
Guinea Pig	> 100,000

Table 1: Pharmacological potency of zilucoplan (IC₅₀) in species tested

Zilucoplan is slowly absorbed in preclinical species after single SC administration, with mean T_{max} ranging from approximately 5 to 8 hours post-dose. The mean elimination half-life in plasma is 7 days in monkeys and humans. The slow elimination kinetics are largely driven by high affinity interaction with the target protein C5 and a much lower affinity interaction with albumin and other plasma proteins. Metabolism of zilucoplan is well-characterized and studies have identified two primary metabolites that occur in similar ratios in both monkeys and humans. Excretion of parent and major metabolites is predominantly hepatobiliary.

The PK/PD relationship of zilucoplan has been extensively investigated in cynomolgus monkeys. An EC₉₀ of 2500 ng/mL was determined in monkeys which translated nearly precisely to the clinical experience in generalized myasthenia gravis trials (Figure).

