5.5 Justification for Dosage

The dosage of 0.3 mg/kg daily is selected for this study based on its well-understood safety and efficacy profile from prior clinical trial experience in neurology. In Ra Pharma's Phase 2 gMG study (RA101495-02.201), the 0.3mg/kg dose demonstrated superior efficacy, greater inhibition of the terminal complement pathway, with a similar safety and tolerability profile as compared with the 0.1 mg/kg and placebo arms. The magnitude and speed of improvement on the primary (Quantitative Myasthenia Gravis Score, QMG) and key secondary (MG Activities of Daily Living, MG-ADL) endpoints were greater with the 0.3 mg/kg dose than the 0.1 mg/kg dose, and both active doses were superior to placebo. The superior efficacy of the 0.3 mg/kg dose was further demonstrated by participants' complete freedom from the need for rescue therapy with IVIG or PLEX in the 0.3mg/kg arm, as compared with a 7% rescue rate in the 0.1mg/kg arm, and a 20% rescue rate in the placebo arm. A higher proportion of participants achieved minimal symptom expression (Vissing 2018), defined as an MG-ADL of 0 or 1, in the 0.3mg/kg arm (35.7%) as compared with the 0.1mg/kg arm (26.7%) and placebo (13.3%).

The dose response seen in the clinical outcome measures is consistent with the known pharmacodynamic effect of zilucoplan that resulted, as expected, in rapid, sustained and complete (97%) inhibition of the terminal complement pathway in all gMG participants receiving the 0.3 mg/kg dose while the 0.1 mg/kg group achieved only submaximal (88%) inhibition of the terminal complement pathway.

[figure not shown]
The once daily dosing interval used in study RA101495-02.201 will be retained in this study because pharmacokinetic simulations indicate that longer dosing intervals cannot achieve adequate exposures and fail to maintain the depth of complement inhibition needed for maximum therapeutic benefit. For example, once every other day dosing is estimated to reduce the zilucoplan trough concentration by approximately 50%, resulting in inadequate pharmacodynamic effect.

The same weight brackets as used in study RA101495-02.201 have been selected for use in this study. Study drug will be provided in prefilled syringes for self-injection using weight bracketed dosing (i.e., participants will be provided prefilled syringes containing fixed amounts of zilucoplan based on their weight, and each fixed amount will cover a range of participant weights).

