6.1.11 Process for Early Terminations

Participants who early terminate from the study and do not complete the protocol will be asked to be seen for an in-person Early Termination Visit and complete a Follow-Up Safety Call. If a participant is not able to be seen in-person, safety assessments and others that can be conducted remotely should be performed.

The in-person Early Termination Visit should be scheduled as soon as possible after a participant early terminates. If the participant early terminates during the placebo-controlled portion of the Regimen, all assessments that are collected at the Week 24 in-clinic visit should be conducted. If the participant early terminates during the OLE phase, all assessments that are collected at the OLE Week 52 in-clinic visit should be conducted. The Follow-Up Safety Call should be completed approximately 40 days after the last dose of study drug.

If the Early Termination Visit occurs approximately 40 ± 3 days after the last dose of study drug, the information from the Follow-Up Safety Call can be collected during the Early Termination Visit, and a separate Follow-Up Safety Call does not need to be completed. If the in-person Early Termination Visit does not occur within 40 ± 3 days of the last dose of study drug, the Follow-Up Safety Call should occur approximately 40 ± 3 days after the last dose of study drug and the Early Termination Visit will be completed after the Follow-Up Safety Call.

Note: Participants should be instructed to continue using effective contraception for at least 40 days after their last dose of study drug.

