6.1 Analysis Sets

The ITT analysis set is henceforth referred to as the Full Analysis Set (FAS) and defined as follows:

- Full Analysis Set (FAS): Participants who were randomized within RGA plus placebo participants from specified regimens, classified according to their randomized treatment assignment. Observations made after premature permanent discontinuation of study drug are included in this sample, should such participants remain on study. Observations completed after regimen data lock are excluded. Participants determined to not meet ALS diagnostic criteria are excluded.

The definition of the STF analysis set is revised as follows:

- Safety Full (STF) Set: Participants who initiated treatment within RGA plus placebo participants from specified regimens who are not known to be ineligible for RGA and who initiated treatment in their respective regimen, classified according to the treatment they actually received. Observations made after premature permanent discontinuation of study drug are included in this sample, should such participants remain on study. Observations completed after regimen data lock are excluded.

An analysis set restricting shared placebo participants to those regimens in which study drug is administered by the same route as RGA is defined as follows:

- Efficacy Common Mode of Administration (ECM) Set: The subset of participants in the FAS analysis set who are in regimens in which study drug is administered by the same route as RGA.

The definitions of the ECC, ERO, STN, and SRO analysis sets are the same as described in the M-SAP with reference to the ITT analysis set now referencing the FAS analysis set. The following analysis set is specific to RGA:

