6.5.13 Pharmacodynamic Biomarker Analyses

Complement functional activity in serum and CSF measured as CH50 values estimated by the sheep RBC hemolysis assay and plasma and CSF C5 levels measured by ELISA will be summarized by treatment group and visit in the ERO sample. Summary statistics will be provided for the values, change from baseline, and percent change from baseline at each scheduled assessment time point.

Population pharmacodynamic or population pharmacokinetic/pharmacodynamic analyses may be conducted. Details of such analyses will be described in a separate DAP and will be performed by UCB Ra Pharma. The results of the analyses will be reported in a separate report and will not be reported in the CSR.

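### PK and complement-activity summaries set no on-treatment condition, so any samples taken after drug was stopped would pull down the exposure and inhibition shown for the dose

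*SAP*

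**What the plan says.** SAP 6.5.12 states that pre-dose concentrations of zilucoplan and its two major metabolites "in plasma and CSF will be summarized by treatment group and visit in the ERO sample". SAP 6.5.13 covers CH50 and C5 in the same way; its sentence ends "measured by ELISA will be summarized by treatment group and visit in the ERO sample". Neither section mentions time since last dose, treatment status or a separate on-drug table.

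The route from ERO to off-drug data runs through SAP 6.1. The ERO definition comes from the Master SAP, "with reference to the ITT analysis set now referencing the FAS analysis set". The same section calls ERO synonymous with ECM, which it defines as a subset of FAS participants. For the FAS it says: "Observations made after premature permanent discontinuation of study drug are included in this sample, should such participants remain on study".

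The protocol makes such samples possible. Section 3.2 counts participants as completing the placebo-controlled period whether on or off drug, and sections 6.1.5, 6.1.7 and 6.1.9 draw PK and PD blood at Weeks 8, 16 and 24. For early terminators in this period, 6.1.11 says "all assessments that are collected at the Week 24 in-clinic visit should be conducted", and the 6.1.9 list includes PK and PD.

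**The concern.** Keeping off-drug data is the right choice for a treatment-policy efficacy estimand. It does not suit a table meant to show what the dose does in people taking it. Protocol 5.5.1 expects the chosen dose to give complete inhibition of C5 and says that PK and PD will help interpret the clinical result. After a null result, the first question will be whether the target failed or the dose under-inhibited. A by-visit table that mixes on-drug troughs with washed-out samples does not answer that cleanly.

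The direction is clear for two measures. In the active arm, off-drug samples can only lower mean drug concentration and mean CH50 inhibition. The population PK and PK/PD modelling that might separate the two is optional and will not be in the clinical study report.

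**Working it through.** **Inputs from the documents**
- Half-life, Protocol 3.1: "The mean elimination half-life in plasma is 7 days in monkeys and humans".
- Every-other-day dosing lowers the trough by approximately 50% (Protocol 5.5).
- Mean inhibition in the gMG study was 97% at 0.3 mg/kg (Protocol 5.5), "while the 0.1 mg/kg group achieved only submaximal (88%) inhibition of the terminal complement pathway".

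**Assumptions, because the documents give no figure**
- f, the share of active-arm samples at a visit that are off drug: 5% to 20%.
- t, the days off drug: 14 to 40.
- On-drug geometric CV: 30%.
- Log-linear decline, with no quantitation floor.

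**Check of the half-life against the protocol's own figure.** In a one-compartment model at steady state, the trough ratio of every-other-day to daily dosing is r/(1+r), with r = 2^(-1/7) = 0.9057. This gives 0.475, a 52% fall against the stated 50% or so. The 7-day figure is consistent.

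**Concentration.** Residual d = 2^(-t/7): 25% at 14 days, 6.25% at 28 days, 1.9% at 40 days. Arithmetic mean ratio = 1 - f(1 - d). Geometric mean ratio = d^f. Log variance = ln(1 + 0.30²) + f(1 - f)(t·ln2/7)², and geometric CV = sqrt(exp(log variance) - 1).

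| f | t (days) | Arithmetic mean ratio | Geometric mean ratio | Geometric CV |
|---|---|---|---|---|
| 5% | 14 | 0.963 | 0.933 | 44% |
| 10% | 28 | 0.906 | 0.758 | 108% |
| 20% | 28 | 0.812 | 0.574 | 165% |
| 20% | 40 | 0.804 | 0.453 | 352% |

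The geometric mean moves far more than the arithmetic mean. If t is counted from the last dose and the comparison is with a trough one day after a dose, the exponent uses t - 1. The 10%, 28-day ratio is then 2^(-0.1 × 27/7) = 0.765 in place of 0.758, which changes nothing of substance.

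**Inhibition, using the gMG 97% as an assumption for ALS.** If inhibition is fully lost off drug, the mean is 97% × (1 - f): 92% at f = 5%, 87.3% at 10%, 78% at 20%. It reaches 88% at f = 1 - 88/97 = 9.3%. That is a worst case. With partial recovery under a sigmoid model with Hill coefficient h, off-drug odds of inhibition are (97/3) × d^h. At 28 days, inhibition is then 66.9% for h = 1, 11.2% for h = 2 and 0.8% for h = 3. With f = 10%, the mean, 0.9 × 97 + 0.1 × that value, is 94.0%, 88.4% or 87.4%.

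**With an on-treatment filter** the dilution factor is 1.00 by construction.

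**The case against.** The strongest reply is that no bias has been shown. The documents give no discontinuation rate, and if nobody sampled is off drug the effect is zero. Several provisions limit such samples: the Early Termination Visit is to be scheduled as soon as possible, participants not seen in person have only assessments that can be done remotely, and remote visits replacing Weeks 8 and 16 collect no PK or PD blood. All of this stands, and it is why the sizes are scenarios only. Long off-drug times are also implausible early: 40 days off drug at Week 8 means stopping by about day 16.

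Pre-dose could be read as excluding someone with no dose to precede. The reading is arguable, but the protocol (8.2, 8.3) and the notes to the SAP schedule use the term to time the draw within a visit, not as an exclusion rule.

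SAP 6.5.12 also reports the median, minimum and number and percentage below quantitation. The median moves little with a 10% off-drug share, and washout would be partly visible. This stands for PK. SAP 6.5.13 names no particular statistics, so the same cannot be said for PD.

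Four stronger inferences are tempting, and the documents do not support them:
- **Early-termination samples are certainly pooled into Week 24.** The protocol schedule combines the two in one column, but the SAP schedule has no early-termination column, and 6.5.13 reports at scheduled time points. The mapping is not shown.
- **The missing 40-day limit is an inconsistency with SAP 6.6.2 to 6.6.6.** That window serves safety tabulation. At 40 days the residual is already 1.9%, so copying it would still admit the 28-day samples above.
- **CSF results shift by a similar size.** The stated half-life is for plasma, and CSF collection is optional.
- **Total C5 shifts in a known direction.** Nothing in the documents establishes one.

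**Conclusion.** The point holds conditionally. As written, the plan permits post-discontinuation samples in the PK and complement-activity summaries. If such samples occur, active-arm plasma concentration and CH50 inhibition will be understated relative to what the dose achieves on treatment. Under the assumed shares and times, the geometric mean falls to between 0.93 and 0.45 of its on-drug value, with 24% lower as the middle illustration.

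These figures rest on the 7-day plasma half-life and on assumed f and t. They also ignore the rule that sets values below quantitation to half the limit; that limit is not given, so very low residuals may not appear as calculated. A reader might infer that the trial will report about 88% inhibition, the level the protocol calls submaximal at the lower dose. That needs 9.3% off-drug samples with complete loss of inhibition, plus the gMG value carried over to ALS, so it marks the edge of the range and is not an expectation.

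The Master SAP was not available and could hold a relevant rule, but 6.5.12 and 6.5.13 do not refer to it for one. The endpoints are exploratory, and efficacy inference is unaffected. This is a cheap improvement.

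**What to change.** In SAP 6.5.12 and 6.5.13:
- Make the lead summary on-treatment. Class participants by treatment actually received, and use samples with a recorded dose within a prespecified interval before the draw. Set that interval for PK purposes; the 40-day safety window would be too long.
- Show post-discontinuation and early-termination samples separately, by days since last dose.
- Keep the all-samples ERO table as a secondary display.

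Apply the same condition to the PK and PD plots by antibody status in Appendix 2. The outputs listed there use SRO, whose definition is in the Master SAP, and the plots state no on-treatment condition.

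The cost is SAP wording and one filter. Last-dose dates are already needed for the exposure calculations in 6.7.2 and the 40-day limits in the safety sections. No sampling, dosing or efficacy estimand changes. The downside is slightly fewer samples per visit in the lead table.
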